Early intervention is critical during the high neuroplasticity period of infancy. The primary condition for early intervention is to identify babies who may have CP. Early detection can be beneficial in terms of starting early intervention during the period when neuroplasticity is high. It is thought that with the prominence of early intervention and protective approaches based on neuroplasticity knowledge, it will be beneficial for babies at risk during development and it will be possible to prevent neurodevelopmental problems and permanent disabilities. The early intervention approach generally includes supporting the development of babies at risk for developmental delay or disability by providing the necessary support, treatment and training starting from the neonatal period and up to 24 months. Early intervention methods have many components and require a multidisciplinary approach. Methods can focus on different approaches according to the determined goals. Physiotherapy and rehabilitation approaches are of great importance in supporting development and improving functional outcomes in early intervention. It is aimed to provide normal sensory input and gain normal functional movements by using the rapid learning ability originating from brain plasticity, and to reach the most independent level that the child can reach in terms of physical, cognitive and psychosocial aspects within the anatomical and physiological deficiencies and environmental limitations. There are many early physiotherapy and rehabilitation approaches that focus on motor development and normalization. Goal-focused therapy is known as an approach that facilitates the participation and adaptation of infants and children with motor developmental delays in daily life activities. Goal-focused neuromotor treatment approach is a set of movements organized around a functional target and provides the formation of environmental movement. Studies on rehabilitation have recently focused on treatment approaches that focus on functionality in accordance with the "Activity and Participation" area of ICF. It is known that babies also have levels of functionality that enable them to participate in daily life activities. In a study where goal-focused neuromotor treatment was applied in early rehabilitation practices, it was stated that this approach can be applied by both the

physiotherapist and the family under the control of the physiotherapist. Family-centered physiotherapy practices have come to the fore in recent years, and are a treatment approach applied by the family that focuses on the environment and what the child can do. Motor reactions are activated by providing normal sensory input. Telerehabilitation is the provision of rehabilitation services by rehabilitation specialists with computer-based technologies and communication tools. It is a developing method that provides rehabilitation services by reducing time, distance and cost barriers and using technological tools. There are previously studies on a portable smart system that is monitored remotely and created for early assessment and intervention.

Although the importance of early physiotherapy approaches is known today, when the literature is examined, it is seen that the number of studies is insufficient and there is no consensus yet on which therapy approach is more successful. No previous study has been found in which family education of risky babies was followed up with telerehabilitation.

2. Objectives

Primary Objective

Evaluate the effectiveness of family-centered, goal-directed early physiotherapy approaches in high-risk infants using telerehabilitation.

Secondary Objectives

- 1. Compare the motor, cognitive, and language developmental progress of infants in telerehabilitation and single-session education groups.
- 2. Assess family satisfaction with telerehabilitation-based physiotherapy.
- 3. Measure neurological outcomes using Hammersmith Infant Neurological Examination (HINE).
- 4. Determine the achievement of individualized treatment goals using the Goal Attainment Scale (GAS).

3. Study Design

Type of Study

A prospective, randomized, controlled trial conducted at the Risky Infants Polyclinic.

Duration

12 weeks, with evaluations conducted at baseline, 4th, 8th, and 12th weeks.

Groups

- 1. **Telerehabilitation-Based Group**: Families received exercise training in the clinic, followed by weekly real-time video-conference sessions (1 day/week) and follow-up phone calls (2 days/week).
- 2. **Single-Session Education Group**: Families received a single session of exercise training in the clinic and were asked to continue the exercises independently.

4. Participants

Inclusion Criteria

- Premature infants (<37 weeks) treated in neonatal intensive care units.
- Infants with neurological abnormalities (muscle hypertonia, hypotonia, overstimulation, abnormal general movements, or cranial ultrasound abnormalities).
- Infants aged 0-12 months (corrected age for prematurity applied).
- Diagnosed as at-risk for motor or developmental delay.
- Infants whose medical treatments are complete and are no longer in neonatal intensive care.
- Families who agree to participate and provide informed consent.

Exclusion Criteria

- Infants with congenital cyanotic heart disease, cystic fibrosis, genetic diseases, or congenital anomalies.
- Infants on ventilators.
- Families unable to attend regular check-ups or weekly communication.
- Infants already enrolled in special education or rehabilitation centers.

5. Outcome Measures

Primary Outcomes

- 1. Changes in neuromotor development using the Hammersmith Infant Neurological Examination (HINE).
- 2. Cognitive, motor, and language development using Bayley III.
- 3. Goal achievement using the Goal Attainment Scale (GAS).

Secondary Outcome

4. Family satisfaction using a custom Satisfaction Survey.

6. Intervention

Training Protocol

- Exercises tailored to neuromotor developmental stages, delivered by experienced pediatric physiotherapists.
- Families instructed to perform exercises for 30-45 minutes, 3 days per week, for 12 weeks.
- Telerehabilitation group received one supervised video-conference session weekly, with phone call follow-ups for the remaining two days.
- Single-session group received instructions during one in-clinic session with no additional follow-up.

7. Data Collection and Tools

Demographics

• Collected using forms capturing infant and family data (age, education, marital status, economic status, number of children, etc.).

Developmental Assessments

- 1. **Bayley III**: Evaluates cognitive, motor, and language development.
- 2. **HINE**: Assesses cranial nerve function, posture, tone, reflexes, and orientation.
- 3. GAS: Tracks individualized treatment goal achievement.

Satisfaction Survey

Assesses family satisfaction with treatment.

8. Statistical Analysis Plan (SAP)

Sample Size Calculation

- Based on a similar study (Pineda et al., 2020), the effect size was calculated as 1.09.
- Using G*Power 3.1.9.2, a total sample size of 24 infants (12 per group) was determined for α =0.05 and power=0.95.

Statistical Methods

• **Descriptive Statistics**: Mean, standard deviation, minimum, and maximum values for quantitative data; frequency and percentage for qualitative data.

• Group Comparisons:

- Mann-Whitney U and chi-square tests for continuous and categorical demographic data.
- Wilcoxon Signed-Ranks Test for pre- and post-treatment comparisons of Bayley III, HINE, and GAS scores.
- **Significance Level**: p<0.05.

9. Ethical Considerations

- The study received ethical approval from the relevant institutional review board.
- Signed informed consent obtained from all participating families.
- Data confidentiality and anonymity maintained throughout the study.

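### The primary objective can be read as testing the physiotherapy itself, but the randomised contrast gives only the added effect of telerehabilitation follow-up over a single education session

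*Combined protocol and SAP*

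**What the plan says.** The primary objective in Section 2 is "Evaluate the effectiveness of family-centered, goal-directed early physiotherapy approaches in high-risk infants using telerehabilitation". The sentence names no comparator. The direct comparison of the arms comes as secondary objective 1: "Compare the motor, cognitive, and language developmental progress of infants in telerehabilitation and single-session education groups".

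Section 3 (Groups) has the families in both arms trained in the exercises in the clinic. For the comparator it says: "Families received a single session of exercise training in the clinic and were asked to continue the exercises independently".

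Section 6 (Training Protocol) opens with two statements that carry no arm label: "Exercises tailored to neuromotor developmental stages, delivered by experienced pediatric physiotherapists" and "Families instructed to perform exercises for 30-45 minutes, 3 days per week, for 12 weeks". It then separates the arms. For one: "Telerehabilitation group received one supervised video-conference session weekly, with phone call follow-ups for the remaining two days". For the other: "Single-session group received instructions during one in-clinic session with no additional follow-up".

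Section 8 (Statistical Methods) gives the developmental and goal scores a Wilcoxon signed-rank test of before against after. The between-group tests it lists are for demographic data.

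**The concern.** An objective should name an effect that the design can identify. Read at face value, this one asks whether family-centred, goal-directed physiotherapy works. Answering that by randomisation needs an arm without the physiotherapy, and there is none.

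The risk lies in the report. Infants enter at 0 to 12 months of age and are followed for 12 weeks, so scores can be expected to rise in both arms through development alone. Small before-after p-values could then be presented as meeting the primary objective. If a between-arm comparison is reported, a null result could be taken as evidence against the physiotherapy although both arms may have benefited. A positive result could be taken as evidence for the physiotherapy when it concerns the follow-up. The design supports none of these conclusions.

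**Working it through.** The plan states no figure for this point. The sample-size figures in Section 8 do not enter the argument. The check compares what each arm receives and then asks which effects can be separated.

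**1. Prescribed home exercise (Section 6, no arm label).**
- Sessions: 3 days per week × 12 weeks = 36.
- Time: 36 × 30 min = 1,080 min = 18 h, up to 36 × 45 min = 1,620 min = 27 h.
- Difference between arms, if the instruction applies to both: none.

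**2. Scheduled remote contact (Sections 3 and 6).**
- Telerehabilitation arm: 1 × 12 = 12 video sessions and 2 × 12 = 24 calls, 36 contacts in all.
- Single-session arm: 0.

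**3. Clinic training (Sections 3 and 6).**
- Single-session arm: one session.
- Telerehabilitation arm: training is given, but the number of sessions is not stated.

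**4. What can be identified.** For the mean change from baseline to week 12, write
- M = change from normal maturation,
- P = effect of being taught and prescribed the home programme,
- F = what the telerehabilitation arm's extra components add to that programme (supervision, calls, contact time, any extra clinic training).

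Then
- change in the telerehabilitation arm = M + P + F,
- change in the single-session arm = M + P,
- difference between arms = (M + P + F) − (M + P) = F.

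There are two arm means and three unknowns. P occurs only in the sum M + P, so no analysis of these two arms separates it from maturation. The visits at weeks 4 and 8 do not help, because maturation and any programme effect build up over the same weeks.

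**5. What the planned tests estimate.** The before-after test addresses M + P + F in one arm or M + P in the other. Either can be clearly above zero when P = 0. The one quantity that randomisation protects, F, has no outcome test in Section 8.

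**6. If the programmes are not identical.** Let the programme effects be P1 (telerehabilitation) and P2 (single session). The difference is then (P1 − P2) + F. This is still a contrast between two ways of providing exercise training. It is not the effect of the physiotherapy against its absence.

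**The case against.** The strongest reply is that the protocol already asks the narrower question. The objective ends by naming telerehabilitation. The background gives as its evidence gap the lack of studies in which education of families was followed up remotely. The arms are named for the two modes, and secondary objective 1 compares them. This largely stands, so the fault is an objective open to two readings, not a flat misstatement. Still, the object of the sentence is the physiotherapy approach, and listing the arm comparison as a separate, secondary aim suggests that the primary aim is something else.

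Three stronger readings are tempting and should not be drawn.

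- *That both arms are documented to receive an identical programme.* This is inferred from an instruction addressed to families in general. The comparator's wording fits it and nothing contradicts it, but no sentence states it. The background also describes goal-focused treatment as something a family can apply under a physiotherapist's oversight, so continuing oversight may be part of the approach and not an addition to it. That would bring the contrast nearer to the objective, but step 6 still applies.
- *That a benefit would show only that follow-up helps families do the exercises.* The video sessions are supervised, so correction, progression or contact time could also produce it. The documents do not identify the mechanism.
- *That low power measures this problem.* Power concerns sample size, and rewording the objective does not change it.

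It can also be said that the missing between-arm outcome test is the more serious defect. That is fair. Adding the test alone, however, would leave a primary objective that the test does not answer.

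**Conclusion.** The point holds in a limited form. The design can estimate the added effect of telerehabilitation follow-up over single-session education. It cannot estimate the effect of the home exercise programme, and the before-after tests cannot supply that effect. Prescribed exercise is 36 sessions in each arm as the document reads, and scheduled remote contact is 36 against 0.

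This rests on two assumptions: that the unlabelled prescription applies to both arms, and that infants of this age develop measurably over 12 weeks. If the first fails, the contrast is more mixed, but the physiotherapy effect remains unidentified.

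The weight is minor to moderate. Allocation, treatment and data collection are unaffected. What changes is which conclusion the trial may validly draw.

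**What to change.** **Section 2.** Restate the primary objective, for example: *to evaluate the effect of adding telerehabilitation follow-up, compared with single-session education alone, on HINE, Bayley III and GAS at week 12 in high-risk infants whose families are taught a home exercise programme.* This keeps all three listed primary outcomes and does not assert that the programmes are identical. Secondary objective 1 then overlaps with it and can be merged.

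**Section 8.** State that:
- the conclusion is drawn from the between-group difference in each primary outcome with its 95% CI, for example a Mann-Whitney test on change scores with a Hodges-Lehmann estimate;
- before-after results within an arm are descriptive;
- neither a positive nor a null between-group result shows whether the exercise programme itself works.

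**Sections 3 and 6.** Say whether the home prescription applies to both arms, and how many clinic training sessions the telerehabilitation arm received, so that the full difference between arms is on record.

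**Cost.** The headline claim becomes narrower and there is a small amount of extra analysis. Treatment, visits, data and sample do not change.

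### Section 2 files HINE, GAS and, by inference, Bayley III under secondary objectives, Section 5 makes the same three measures primary outcomes, and no text says which ranking governs

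*Combined protocol and SAP*

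**What the plan says.** Section 2 states a single leading aim, which reads "Evaluate the effectiveness of family-centered, goal-directed early physiotherapy approaches in high-risk infants using telerehabilitation". Below it stand four objectives ranked as secondary. The first of these is worded as a contrast of the two arms: "Compare the motor, cognitive, and language developmental progress of infants in telerehabilitation and single-session education groups". The second concerns how satisfied the families are. The third brings in the neurological examination: "Measure neurological outcomes using Hammersmith Infant Neurological Examination (HINE"). The fourth deals with the goals set for each infant: "Determine the achievement of individualized treatment goals using the Goal Attainment Scale (GAS").

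Section 5 ranks three outcomes as primary. It begins with the neurological examination, given as "Changes in neuromotor development using the Hammersmith Infant Neurological Examination (HINE"). Next comes the developmental scale, given as "Cognitive, motor, and language development using Bayley III". Last is the goal scale, given as "Goal achievement using the Goal Attainment Scale (GAS"). Its only secondary outcome is family satisfaction, measured by a survey made for the study.

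Section 3 describes a randomised controlled trial with two groups, assessed at baseline and at weeks 4, 8 and 12. Section 8 plans Mann-Whitney U and chi-square tests for demographic data and Wilcoxon signed-ranks tests for pre-post scores on Bayley III, HINE and GAS. It designates no primary endpoint, testing order or division of alpha, and it does not tie the effect size of 1.09 to any outcome.

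**The concern.** The rank of an outcome tells the reader which results the trial was set up to confirm and which are supportive. Here the same measures have one rank as objectives and another as outcomes. A reader of the final report could not tell from the plan whether, say, a GAS result answers the main question or a subsidiary one. Authors would have some textual support for either description after seeing the data.

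The second matter is the question itself. The control arm exists so that infants whose families receive telerehabilitation can be compared with infants whose families receive a single session. Infants develop over 12 weeks in any case, so change within one arm cannot isolate the effect of telerehabilitation. Yet the only objective that explicitly compares the arms stands below the primary objective, which does not say what is measured, against what, or when.

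**Working it through.** No figure in the plan needs reproducing. The check sets the two lists side by side.

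| Measure | Section 2 | Section 5 | How the link is made | Same rank? |
|---|---|---|---|---|
| HINE | secondary objective 3 | primary outcome 1 | named in both | no |
| Bayley III | secondary objective 1 | primary outcome 2 | inferred from its domains | no |
| GAS | secondary objective 4 | primary outcome 3 | named in both | no |
| Family satisfaction | secondary objective 2 | secondary outcome | named in both | yes |

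**Strength of each link.** HINE and GAS need no interpretation. Secondary objective 1 does not name Bayley III. It names motor, cognitive and language progress, the three domains that Sections 5 and 7 assign to Bayley III, and no other listed tool is described as covering cognition or language. The inference is strong but remains an inference, and the motor part could also overlap with HINE.

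**Count.** Of the four measures, 3 have conflicting ranks and 1 agrees. The 3 are all of the primary outcomes in Section 5. Two of the conflicts are explicit and one is inferred.

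**Does any other text settle it?**

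- The primary objective names no instrument, comparator or time point, so it does not claim any of the three measures.
- Section 8 puts the three measures on one line without ranking them, and names no primary endpoint.
- The sample size calculation could have revealed the intended primary outcome, but its effect size is attached to none.
- No statement says that one section takes precedence.

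**Where is the comparison of arms?** Among objectives and outcomes, only secondary objective 1 is worded as one. In Section 8, the only tests whose between-group use is clear are those for demographic data. The three outcome measures get paired pre-post tests alone. Rewording Section 2 without touching Section 8 would therefore leave the new primary objective with no matching analysis.

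**What alignment would leave open.** Suppose the three Section 5 measures are each tested at 0.05 and any success counts. The chance of at least one false positive, if the tests were independent, is 1 − 0.95³ = 0.143, and it cannot exceed 3 × 0.05 = 0.15. If the three Bayley III domains count separately there are five scores: 1 − 0.95⁵ = 0.226, at most 0.25. These figures concern multiplicity, a separate matter. They show only that agreeing the ranks does not by itself prevent selective emphasis, and they add nothing to the size of the present point.

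**The case against.** The best defence is that objectives and outcomes are different lists. Only Section 5 ranks outcomes, and it does so plainly. Section 2 can be read as one umbrella aim, effectiveness, followed by its component aims. On that reading the three Section 5 primaries are the measures of effectiveness, and Section 8 is consistent in treating them together. Much of this stands: an author who demoted one of the three would contradict Section 5. It does not remove the conflict, because Section 2 labels the objectives that name HINE and GAS as secondary rather than as components of the primary one. One of the two sections has to change.

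Three stronger readings are tempting, and the documents do not support them.

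- *That the status of every result is open.* Family satisfaction is secondary in both sections.
- *That the randomised comparison is formally not the primary question.* Section 3 describes a randomised controlled trial with two defined arms, and evaluating effectiveness in such a design can reasonably be read as comparative. The text fails to say so, which is a drafting gap and not a demotion.
- *That outcomes can be freely promoted or demoted under the protocol, or that this has happened.* Section 5 is explicit about outcomes, and nothing in the documents shows selective reporting. They leave room for it without licensing it.

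**Conclusion.** The point holds as an inconsistency between Sections 2 and 5 that leaves the confirmatory status of the HINE, Bayley III and GAS results ambiguous. It affects all three primary outcomes, two by name and one by inference from shared domains, and it does not affect satisfaction. The primary objective is too general to resolve it.

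The conclusion rests on the wording alone and on one assumption: that secondary objective 1 refers to Bayley III. If that were wrong, the conflict would still stand for HINE and GAS. The point does not depend on the sample size, on any error-rate figure, or on how the authors will report. It is a defect of specification that matters for interpretation and is cheap to correct.

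**What to change.** 1. State that the ranking in Section 5 governs.
2. Reword the primary objective as the comparison of the telerehabilitation and single-session groups on the Section 5 primary outcomes at the end of the 12-week treatment period. Week 12 is already a scheduled evaluation. Naming it is a choice the plan has yet to make, since Section 8 speaks only of pre- and post-treatment.
3. Move objectives 1, 3 and 4 under the primary objective, each worded as a between-group comparison and with Bayley III named. Leave satisfaction as the only secondary objective.
4. Change Section 8 to match. Make the primary analysis of each of the three outcomes a between-group test, for example Mann-Whitney U on the change from baseline to week 12. Keep the Wilcoxon pre-post tests as descriptive results within each arm.
5. Make the change before outcomes are compared by arm. Sections 3, 6 and 9 describe some procedures in the past tense, and the documents do not show whether that is still possible. If the comparison has already been made, report the rank conflict and how it was resolved.

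The cost is a short wording amendment and one extra planned test per outcome, with no new visit or assessment. The change does not settle multiplicity among the three primary measures, which needs its own rule.

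### Weeks 4 and 8 have no stated role in the outcome analysis, and the single pre/post test drops any infant without a post-treatment value

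*Combined protocol and SAP*

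**What the plan says.** Section 3 (Study Design, Duration) gives the schedule as "12 weeks, with evaluations conducted at baseline, 4th, 8th, and 12th weeks": one baseline and three follow-up assessments. It does not say which instruments are given at which visit.

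Section 8 (Statistical Methods) names one test for the primary outcomes: "Wilcoxon Signed-Ranks Test for pre- and post-treatment comparisons of Bayley III, HINE, and GAS scores". The between-group tests are "Mann-Whitney U and chi-square tests for continuous and categorical demographic data", so they are not assigned to outcomes. Descriptive statistics are "Mean, standard deviation, minimum, and maximum values for quantitative data; frequency and percentage for qualitative data", with no restriction to particular visits.

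The post-treatment time point is not tied to a named week. Section 6 implies week 12: "Families instructed to perform exercises for 30-45 minutes, 3 days per week, for 12 weeks". No analysis population, missing-data rule or dropout allowance is stated. The nearest text is an exclusion criterion in Section 4: "Families unable to attend regular check-ups or weekly communication".

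**The concern.** The first secondary objective is to compare developmental progress between the groups, and the first primary outcome is change in HINE. Serial assessments are the natural data for both, yet the only outcome test takes one value before and one after. A signed-rank test needs both members of the pair, so an infant seen at baseline, week 4 and week 8 but not at the end contributes nothing to it.

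With 12 infants per arm, each loss is 1/12, or about 8%, of an arm. Contact is also unequal by design: the telerehabilitation families have three contacts a week, while the single-session families have no further follow-up. Unequal dropout is therefore plausible, although the documents do not report any. If it were related to progress, an arm comparison based on completers would be biased. Because the SAP is silent, the handling of a missing final value could also be chosen after the data are seen.

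**Working it through.** **1. The plan's own figure.** Section 8 states that "the effect size was calculated as 1.09" and that "a total sample size of 24 infants (12 per group) was determined for α =0.05 and power=0.95". The type of effect size and the sidedness are not given.
- Two-sample t-test, d = 1.09, power 0.95: 19 per arm one-sided, 23 per arm two-sided. At 12 per arm, power is 0.83 one-sided and 0.72 two-sided.
- One-sided signed-rank test with a paired effect of 1.09: 12 per group (power 0.963). Two-sided it needs 14 (power 0.915 at 12).

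So 12 per group reproduces only as a one-sided, within-group calculation. That is a separate point. Here 1.09 and 12 per arm serve only as a common scale.

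**2. Loss of pairs from the planned test.** Signed-rank power, two-sided, paired effect 1.09, as infants lack a final value:

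| Infants with a pair | 12 | 11 | 10 | 9 |
|---|---|---|---|---|
| Power | 0.915 | 0.885 | 0.845 | 0.793 |

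**3. Complete data: where the gain in an arm comparison comes from.** Assumptions: unit variance at each visit, compound symmetry with correlation ρ = 0.5, an effect growing linearly to 1.09 SD at week 12, and a two-sided test.
- Variance of change: 2(1 − ρ) = 1.00. Variance after baseline adjustment: 1 − ρ² = 0.75.
- Noncentrality = d·√(n/2)/√variance. For change: 1.09 × √6 / 1 = 2.67. For ANCOVA: 2.67 / √0.75 = 3.08.
- Ignoring one degree of freedom, ANCOVA on 12 per arm is worth a change-score analysis on 12/0.75 = 16 per arm.
- Simulated power: Mann-Whitney on change 0.68, ANCOVA 0.82, longitudinal week-12 contrast 0.85.

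ANCOVA uses no interim visit, so the step from 0.68 to 0.82 is not due to weeks 4 and 8. In generalised least squares with a common baseline mean and no missing data, weeks 4 and 8 add nothing to the week-12 contrast. The last 0.03 reflects the compound-symmetry model pooling variance over visits, plus simulation error.

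**4. Week 12 missing.** The documents give no dropout rate, so 1 to 3 per arm is assumed, with ρ from 0.5 to 0.8 under compound symmetry or AR(1).

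| Missing week 12, per arm | Completers | Effective n using weeks 4 and 8 |
|---|---|---|
| 1 | 11 | 11.2–11.5 |
| 2 | 10 | 10.3–10.9 |
| 3 | 9 | 9.4–10.3 |

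The model recovers about 13% to 49% of the lost information. Simulated power with 2 per arm missing at random, ρ = 0.5, compound symmetry: ANCOVA 0.74, longitudinal contrast 0.80. The interim visits' own share is thus about 0.06.

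**5. Dropout that depends on progress.** Suppose the 2 or 3 control infants with least progress by week 8 miss week 12 (ρ = 0.5). The completer estimate of the arm difference in change falls from 1.09 to 0.95 or 0.89, that is by 0.14/1.09 = 13% or 0.20/1.09 = 18%. The longitudinal model stays at 1.08 to 1.10.

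**6. Covariance choice.** Simulated type I error at nominal 0.05 for the week-12 contrast from a random-intercept (compound-symmetry) model, 12 per arm:
- Compound symmetry true: 0.047.
- AR(1) true, correlation 0.7 to 0.8: 0.089 to 0.096 in one simulation, 0.085 to 0.137 in another.
- Random slopes true: 0.107.

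ANCOVA stayed at about 0.04 to 0.055.

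**The case against.** A single end-of-treatment endpoint is a legitimate choice, and interim visits may serve monitoring or goal review. That stands: the defect is not the week-12 endpoint but the unstated role of weeks 4 and 8 and the absent rule for a missing final value.

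A reader might infer that two of the three follow-up assessments are discarded and that an infant missing week 12 is lost entirely. The documents do not support this. Descriptive statistics could cover the interim visits, no instrument is tied to weeks 4 and 8, and a last-available value is not ruled out because post-treatment is undefined. The infant's baseline data would remain in any case.

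A reader might also infer that unused interim data cost substantial power even with complete follow-up. Steps 3 and 4 show otherwise. A linear-trend effect did reach 0.90, but that is a different estimand under assumed linear growth. When the effect appeared only at week 12, it fell to 0.71, below ANCOVA at 0.82.

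Mann-Whitney on change is not the planned outcome test either, so the 0.68 describes a substitute between-group test. The lack of any planned between-group outcome test is a separate matter, which the fix below happens to address.

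Finally, a repeated-measures model on 24 infants carries real risk. Step 6 bears this out and determines the recommended covariance. A small-sample degrees-of-freedom correction does not repair a wrong covariance structure.

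**Conclusion.** The point holds in a limited form. Scores at weeks 4 and 8 have no stated inferential use, the only outcome test has no arm term, and an infant without a post-treatment value drops out of it with no stated rule. A baseline-adjusted week-12 arm contrast that uses all collected follow-up is better and needs no new data.

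The gain is mostly baseline adjustment (about 0.68 to 0.82 with complete data). The interim visits add about 0.74 to 0.80 when 2 per arm lack week 12, and they guard against a bias of roughly 13% to 18% in the progress-related dropout scenario. All of this rests on assumed values: d = 1.09 read as a between-group effect, ρ = 0.5, compound symmetry and the dropout patterns. The unstructured model recommended below was not itself simulated, so the longitudinal power figures should not be taken as promised for it. The point deserves a change to the SAP but does not by itself invalidate the trial.

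**What to change.** 1. Define post-treatment as week 12, and state which instruments are used at each visit and what weeks 4 and 8 are for.
2. Make the baseline-adjusted week-12 arm difference with 95% CI the primary estimate for each score.
3. For every score measured at the interim visits, estimate that difference from all visits in a repeated-measures model with visit, arm-by-visit, a common baseline mean (or baseline as covariate) and corrected age. Use an unstructured covariance with a Kenward-Roger correction, not a random intercept alone.
4. Pre-specify the fallback if the model does not converge: a simpler structure with small-sample robust standard errors, or week-12 ANCOVA.
5. Include every randomised infant with any follow-up assessment.
6. Keep ANCOVA and Mann-Whitney on week-12 change as sensitivity analyses. If a score is not measured at weeks 4 and 8, week-12 ANCOVA is its primary analysis.

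Cost: SAP wording and modest analysis work, with no extra visits or data. The main downside is the covariance assumption with only 24 infants. An unstructured matrix over four visits has 4 × 5 / 2 = 10 parameters, or 3 × 4 / 2 = 6 with baseline as covariate, so the fallback may well be needed. If outcome data have already been examined, the revised analysis should be labelled as specified afterwards.
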